Clearing the battlefield quickly and providing the best care possible for the wounded is a priority for military medics. The primary mode of patient transport whether by land, sea or air is on a litter (NATO litter for USAF aircraft)^{3,6,7}. Litter stands provide the support necessary to transform a litter into an operating room (OR) table or hospital bed. Patients can spend several hours and/or days resting on a litter in a field hospital, or in transit to the next level of care⁶⁻⁷. Injuries or illness that prevents patients from normal movement and repositioning place them at increased risk of pressure ulcer development⁸. Specialty beds and mattresses are available in most hospitals to help prevent pressure ulcer development in patients. Unfortunately, these products are not currently available for contingency or aeromedical evacuation (AE) operations. The purpose of this study is to measure peak skin interface pressures and the total area of the body exposed to skin interface pressure above 30 mm Hg at different areas of the body in the supine position on two different support surfaces applied to a standard North Atlantic Treaty Organization (NATO) litter (NSN: 6530-01-380-7309) and a Raven 90C Litter (NSN6530-01-432-5114). The Raven 90C is the official litter for the U.S. Navy. It is approved for flight on USAF aircraft. It can be easily folded for storage and transport to remote settings. The support surfaces are the Warrior Evacuation Litter Pad (WELP) and the Dolphin Fluid Immersion Simulation Stretcher System (FIS). In theory, mattresses that reduce and/or minimize pressure on the capillary bed's perfusion can help reduce pressure related injury such as pressure or decubitus ulcer development. Skin interface pressure measurements using a pressure mapping system along with transcutaneous oxygenation readings will allow us to determine these differences between support surfaces. A better understanding of skin interface pressure associated with the litter support surfaces is vital for military nurses to develop and implement preventative interventions to reduce pressure ulcer development in our patients. In addition, this study will provide information to help determine the usefulness and feasibility of incorporating the fluid immersion system (FIS) as a litter support surface.

5. Category of Study and Risk Assessment:

5.1. Category of Study:

Medical Utilization Prevention Medical Readiness Diagnosis/Treatment/Other

5.2. Proposed Risk:

Pressure ulcers (PU) are defined by the United States National Pressure Ulcer Advisory Panel (NPUAP) and the European Pressure Ulcer Advisory Panel (EPUAP) as "localized injury to the skin and/or underlying tissue usually over a bony prominence, as a result of pressure, or pressure in combination with shear"⁸⁻⁹. Pressure ulcers develop when soft tissue is compressed between a bony prominence and a hard surface for an extended period of time. In an alert person with normal motor and sensory function, nociceptors sense increased pressure and signal the brain. As a result of the signal, the person naturally repositions. But if a patient is anesthetized, has a condition that impairs their ability to reposition (such as decreased level of consciousness or paralysis), or is taking opioids that decrease the pain messages, this protective mechanism is blunted or completely disappears raising the risk of pressure ulcer development^{9, 18, 39-40}. While PUs can appear in as little as 24 hours, it can take as long as five days before they appear^{10, 13, 20, 35}. Prevention of PU development is extremely important as they lead to decreased quality of life, increased length of hospital stay, pain, increased morbidity and decreased mortality¹. Pressure ulcers are both high cost and high volume adverse events. Although

For Protocol Office use only:

Protocol title: NATO Litter: Fluid Immersion System
(FIS) versus Traditional Mattress for Pressure Dispersion
FDG20160005H wAmd5

(investigator names redacted 23 Jan 20)

DGMC Human Research Protocol

multiple factors contribute to ulceration such as nutritional status, level of bladder/bowel control (continence), physical condition, level of consciousness, immobility, exposure to pressure, shear and friction forces, the key factor in tissue damage is unrelieved pressure^{2, 5, 9, 18, 20, 27}. Therefore, surfaces that can redistribute pressure across the body are important¹⁹.

Mattress Surfaces

In the past, purchasing hospital mattresses was a simple task carried out by housekeeping staff or supply custodians. Now with advanced clinical understanding of how a mattress can effect skin/wound development and healing, mattress selection has increased in importance^{14, 17, 19-22, 32, 36}. The choice of a medical mattress must be made with a clinical focus on therapy and treatment. A variety of support surfaces are on the market. Many manufacturers claim that their product relieves or reduces the external forces that contribute to pressure ulcer development.

Fluid Immersion System (FIS)

The U.S. Navy trained dolphins for military exercises to use their sophisticated sonar abilities. However, the transport of dolphins outside of water subjects them to the vertical shear forces of gravity causing internal organ trauma and circulatory distress. An Auto Vector surface was created in response to minimize the effects of the gravity's shearing forces. Biologics Inc. began development of a Fluid Immersion Simulation (FIS) software technology to mimic the fluid buoyancy of a body in salt water. This new technology was further developed for medical patients. Joerns Healthcare now offers the health care industry hospital beds, operating room tables, stretchers and wheelchairs with this FIS technology. Dolphin FIS software uses complex algorithms, a microprocessor and sophisticated dynamic pressure waveform analysis to precisely adjust the density of the surface for the unique anatomical features of the patient. It is reported to continuously monitor the patient's weight, three dimensional (3D) surface area and movements to automatically calculate the exact settings to effectively manage the pressure of the patient's body in the medium. The result is that the patient is truly floating, cradled in a simulated fluid environment and suspended in a near neutrally buoyant state (according to the manufacturer/product developer). Distortion to the body is minimized and orientation of bone, muscle and subcutaneous tissue is normalized (using volumetric pressure redistribution). Dolphin FIS technology is easy to use. There's virtually no programming, no manual data input, and no need for caregiver/staff intervention. Simply plug it into the wall and place the patient on the Auto Vector (mattress) surface. Auto Vector "Dolphin" Stretcher Mattress with FIS is customizable to any stretcher regardless of make or model⁴¹⁻⁴². Therefore, this technology could be designed to fit a NATO litter with or without the Special Medical Emergency Evacuation Device (SMEED) commonly used to support equipment with critical care aeromedical transport team (CCATT) patients. It also remains inflated up to eight hours with full operation under its own internal battery supply. This is a FDA approved commercially available product.

For Protocol Office use only:

Protocol title: NATO Litter: Fluid Immersion System
(FIS) versus Traditional Mattress for Pressure Dispersion
FDG20160005H wAmd5

(investigator names redacted 23 Jan 20)

DGMC Human Research Protocol

A Cochrane systematic review and meta-analysis of studies focusing on the effectiveness of pressure redistribution support surfaces in the prevention of pressure ulcers found good evidence that higher specification foam mattresses, sheepskin and some overlays are effective in preventing pressure ulcers. However, the benefits of high-tech constant low pressure and alternating pressure for pressure ulcer prevention are still unclear. Further research is recommended^{19,21}.

Limited data exists on blood flow perfusion using the Dolphin FIS technology^{32,33}. Kohanzadeh et al. (2009).³³ investigated the effect of the FIS stretcher system on the body's cutaneous microcirculation using laser doppler flow instrumentation in 10 healthy subjects on a hospital gurney. Skin perfusion was measured at pressure points of the bilateral shoulders of each subject. This technique allowed investigators to monitor the dynamic changes in the microcirculation in real time. A significant difference was observed in perfusion of 90.52% vs. 22.31% on a regular gurney mattress and Dolphin FIS, respectively. This significant improvement in microcirculation using the Dolphin FIS technology when compared to regular gurney foam support mattress may result in reduced pressure sores and greater patient comfort. These results are supported from observations by Evers et al. (2009)³². Researchers found significantly improved blood flow on the Dolphin FIS when compared to the standard gurney/bed despite such encouraging results, the studies were small scale with limited sample sizes. Therefore, further study with this new FIS technology is recommended³³.

NATO Litter

Very little literature is published on the use of NATO litters and/or litter padding and pressure ulcer development^{37,38}. The interface pressure areas were compared in two subjects on the screw and plate strip NATO litter and tacked canvas NATO litter (NATO 6530-99-138-8737). Both litter versions were evaluated without mattresses. Pressure varied greatly on the screw and plate litter than the tacked litter. Pressure was highest when the subject's sacrum rested over a ridge on the screw and plate stretcher (138 mmHg and 104 mmHg) compared with 38 and 43 mmHg on the tacked litter. The authors concluded that the tacked litter might possibly be better than the screw and plate version³⁸.

In a larger study, investigators explored the differences in skin interface pressures of subjects on the NATO litter (the standard canvas NATO litter with wooden poles, NSN 6530-00-783-7905)³. Thirty-two subjects (18 women/14 men, ages 18-55) underwent skin interface pressure measurements on multiple locations over the body (bilateral heels, calves, buttocks, scapula, elbows, occiput and sacrum) using the X Sensor pressure mapping system. The measurements were taken with subjects on various litter configurations: the litter without any padding, with a military wool blanket for padding, with the standard aeromedical evacuation (AE) litter pad and with the Baxter Maxifloat Mattress. Pressure measurements were taken with the subjects in various physical positions (supine, 30° degree lateral position with 0° degree backrest elevation and supine with 40° degree backrest elevation) for each litter iteration (with and without the padding). There was a significant and progressive decrease in peak pressures between the

For Protocol Office use only:

Protocol title: NATO Litter: Fluid Immersion System
(FIS) versus Traditional Mattress for Pressure Dispersion
FDG20160005H wAmd5

(investigator names redacted 23 Jan 20)

DGMC Human Research Protocol

litter with no padding and the litter with the AE mattress. The greatest pressure decrease was found with the Maxifloat mattress. The wool blanket added the least amount of pressure reduction (mainly in the region of the buttocks). The AE mattress reduced pressures in all areas measures when compared to the litter with no padding and the litter with the wool blanket. The Maxifloat mattress reduced pressure areas on an average of 20 mmHg more than the AE mattress. However, peak pressures over the high risk body areas (e.g. occiput, heels and sacrum) were all higher than the critical closing pressure (30 mmHg). This finding indicated a potential risk for pressure ulcer development. These peak pressures were also higher than those on the Maxifloat mattress. Elevating heels, turning or repositioning are recommended for patients at risk for pressure ulcer development. Unfortunately on an AE mission with critically injured and/or ventilated patient, turning and repositioning may not be possible. The investigators recommended further study using litter stanchions, the Raven litter and a mesh decontamination litter. They also recommended that transcutaneous oxygenation and blood flow be measured³.

Pressure Mapping

Pressure mapping systems determine the actual pressure between the body surface and the resting platform (mattress, bed, seat cushion, etc.). The mapping system consists of a thin, sensor-filled mat with monitoring capabilities placed between the patient and the surface he's lying, sitting, or standing on. The sensors convey interface pressures to a computer, which produces a color-coded image of the pressure distribution on a computer screen. Different colors represent different pressure ranges. Typically, the colors blue and green represent lower pressure ranges while yellow, orange, and red indicate progressively higher pressure levels¹⁵. Although the amount of pressure and/or duration of pressure causing skin damage remain equivocal, evidence suggests that 30 mm Hg be considered the threshold for pressure measurement. Pressures ≥ 30 mmHg is believed to exceed capillary filling pressure, causing ischemia and skin damage³⁵.

6.2. Relevance/Significance:

The war wounded are not immune to pressure ulcer development and unfortunately, as a result of the severity of their injuries and the process of medical evacuation, the risk for pressure ulcer development in wounded personnel returning from Iraq and Afghanistan has increased. Furthermore, the risk for pressure ulcers was identified, with one of the major military treatment centers noting an increase in the incidence of pressure ulcers among the returning wounded^{7, 43}. Pressure ulcers are characteristically more prevalent in adults ≥ 65 years of age due to changes associated with advanced age and failing health. They are also associated in individuals with limited or no mobility such as spinal cord injuries. The Global War on Terror has created a new population of young polytrauma patients with new challenges for the military health care system, one of which is preventing pressure ulcer development. Their injuries were most likely sustained

For Protocol Office use only:

Protocol title: NATO Litter: Fluid Immersion System
(FIS) versus Traditional Mattress for Pressure Dispersion
FDG20160005H wAmd5

(investigator names redacted 23 Jan 20)

DGMC Human Research Protocol

in a hostile and austere environment where care was focused primarily on immediate life-threatening interventions and medical evacuation to a higher level of care. Medical evacuation most likely occurred on a NATO field litter, which can produce peak interface pressures greater than 30 mm Hg over bony prominences³ and limit tissue perfusion³⁵. The combination of poly-trauma, traumatic brain injury, hypoperfusion, sedation, cervical collars, and medical evacuation places injured individuals at high risk for pressure ulcer development early in the care continuum. Finding ways to reduce or eliminate pressure ulcer development is a patient safety/quality of care issue. Interventions to help reduce/eliminate this problem as early in the continuum of care as possible would improve patient safety outcomes and raise quality of care. In the operational setting, that starts with the transport litter.

Purpose:

The purpose of this study is to measure peak skin interface pressures and the total area of the body exposed to skin interface pressures above 30 mm Hg while subjects are in the supine position. Two different support surfaces will be applied to a standard North Atlantic Treaty Organization (NATO) litter (NSN: 6530-01-380-7309) and a Raven 90C Litter (NSN6530-01-432-5114). The support surfaces are the Warrior Evacuation Litter Pad (WELP) and the Dolphin Fluid Immersion System (FIS). These pressure measurements along with transcutaneous oxygenation readings will allow us to determine differences between support surfaces.

This research protocol has one major aim:

To determine the difference in the pressure redistribution qualities between the WELP and the Dolphin FIS

There are also two secondary aims:

1. To determine the difference in the pressure redistribution qualities of the WELP when used as the mattress on the NATO litter and Raven litter.
2. To determine the difference in the pressure redistribution qualities of the Dolphin FIS when used as the mattress on the NATO litter and Raven litter.

6.3. Hypotheses or Research Questions or Objectives:

Research Questions:

1. Is there a significant difference in pressure redistribution qualities between the WELP and Dolphin FIS mattresses on the NATO Litter?
2. Is there a significant difference in the pressure redistribution qualities between the WELP and Dolphin FIS mattresses on the Raven Litter?

3. Is there a significant difference in the pressure redistribution qualities of the WELP between the NATO and Raven 90C litters?

4. Is there a significant difference in the pressure redistribution qualities of the Dolphin FIS mattress between the NATO and Raven litters?

Hypotheses:

1. Pressure redistribution qualities will be greater for subjects on the Dolphin FIS than the WELP in the supine position.

2. There is a difference in pressure distribution between men and women, given BMI level (high, ideal) for subjects on the WELP padded NATO with Raven litters.

3. There is a difference in pressure distribution between men and women, given BMI level (high, ideal) for subjects on the Dolphin FIS padded NATO with Raven litters.

4. There is a difference in pressure redistribution qualities of the WELP for subjects on the NATO and Raven litters.

5. There is a difference in pressure redistribution qualities of the Dolphin FIS for subjects on the NATO and Raven litters.

Outcome measures:

Pressure Redistribution: Peak Pressure Index & Total Surface Area (TSA)

Pressure redistribution qualities will be measured in mmHg using XSensor X3 pressure mapping technology. To minimize the risk of a faulty sensor or false reading over one sensor, the average of eight cells around the region will be recorded and referred to as the Peak Pressure Index (PPI). Peak interface pressure is the highest average pressure (mm Hg) measured over vulnerable bony prominences (occiput, sacrum, and bilateral scapula, buttocks, and heels).

TSA will be measured in centimeters squared (cm²). Vulnerable bony prominences with skin interface pressures exceeding 30 mm Hg will be documented.

Tissue Perfusion: Transcutaneous Oxygenation:

Transcutaneous partial pressures of oxygen (tcpO₂) in millimeters of mercury (mmHg) is non-invasive measurement/monitoring of the skin's surface partial pressure of oxygen. For purposes of this study, tcpO₂ measurements will be captured in the scapula region and expressed in mm Hg. Transcutaneous tissue perfusion has been used as the index of tissue viability by several groups^{44,45,49}. From the early work of Seiler et al. (1997, 1983)^{47,48}, a baseline tcpO₂ value for

For Protocol Office use only:

Protocol title: NATO Litter: Fluid Immersion System
(FIS) versus Traditional Mattress for Pressure Dispersion
FDG20160005H wAmd5

(investigator names redacted 23 Jan 20)

DGMC Human Research Protocol

uncompressed soft tissue was established as 80 mmHg (10.7kPa). When tissue is subjected to pressure load, the tcpO₂ decreases dramatically due to occlusion of the blood flow underneath the pressure point. Bogie et al. (1992)⁴⁶ suggested a threshold value of tcpO₂ as 30 mmHg to indicate a significantly higher risk to tissue viability below this value. Bogie et al. (1995)⁵⁰ later suggested the threshold value for tcpO₂ as 44 mmHg.

Body Mass Index (BMI) will be obtained for men and women obtained using tools (BMI calculator and/or tables) from the U.S. Department of Health and Human Services, National Institutes of Health, Heart, Lung and Blood Institute. For the purposes of this study, BMIs will be categorized as high or ideal.

Ideal = Normal BMI of 18.5-24.9

High = Overweight BMI of 25 -29.9 and Obese BMI of 30 and above

BMI Calculator can be found at

http://www.nhlbi.nih.gov/health/educational/lose_wt/BMI/bmicalc.htm

BMI tables can be found at

http://www.nhlbi.nih.gov/health/educational/lose_wt/BMI/bmi_tbl.htm

Demographic characteristics will be obtained to describe the study sample.

6.4. Research Design and Methods:

Research Design

This protocol is a Quasi Experimental Cross Factor study. The subject sample is nonrandomized. Subjects will be their own control and have repeated measurements to compare baseline and supine transcutaneous oxygenation levels on four different surface combinations. Interface pressure will be measured using the XSensor X3 Pressure Mapping System 32x 80 medical mattress, ½" resolution, 10,240 sensing points, 5-50 & 10-200mmHg pressure range. The XSensor system uses force transducer arrays, which consist of a grid of transducers with half inch square resolution aligned in a matrix which is embedded in a 32 x 80 thin mat which is placed under the subject to map the entire body. Calibration of the pressure mapping system will be performed before and after each participant and the amount of drift evaluated. Mattress will be sanitized with disinfectant wipes between each participant. The sequence of the four surface combinations will be randomly assigned using Research Randomizer at <https://www.randomizer.org> for each participant. A stratified sampling scheme will be used to ensure adequate representation of the following attributes: gender, normal weight and overweight or obese as determined by BMI.

Healthy adults with authorized access to Travis AFB will be offered the opportunity to participate in this study. After the consenting process is completed, subjects will be

For Protocol Office use only:

Protocol title: NATO Litter: Fluid Immersion System
(FIS) versus Traditional Mattress for Pressure Dispersion
FDG20160005H wAmd5

(investigator names redacted 23 Jan 20)

DGMC Human Research Protocol

scheduled for study participation. If time allows, the subject may be able to participate directly after completing the consent process. The subject will be assigned an identification (ID) number which will be annotated on the consent form and all of the data collection documents. The subject's name will only appear on the study consent form. All other study documents and data collection forms will only have the subject's ID number and no other personally identifiable information (PII). Subjects will be asked to wear a nonrestrictive single layer of garments for the study. They will be given a hospital gown to wear over the upper body. This will allow the study staff easy access to the subject's back for application of the transcutaneous oxygenation transducers. Females will not be required to remove their bra. Subjects will be asked their age and have their height and weight measured by a study team member. They will also be asked their litter and mattress preferences at the end of the study. The study portion should take approximately two hours to complete and can be broken into segments for multiple visits if necessary to accommodate a subjects schedule.

Prior to skin oximetry readings, subjects will be asked to refrain from exercising, smoking and drinking caffeinated beverages for at least two hours before data collection. These readings will be performed using specialized equipment from the DGMC hyperbaric clinic. Bilateral transcutaneous oxygenation will be obtained using a radiometer or Perimed™ instrument and by placing electrochemical transducers bilaterally in the region of the subject's scapula. The transducers and probes will be affixed to the skin after the site has been cleaned. To increase permeability of the skin to oxygen at the measuring sites, transducers will be heated to 44° C (111.2°F). After a calibration period of approximately 10-15 minutes, a constant transcutaneous partial pressure of oxygen will be obtained and recorded onto the patient data sheet. Baseline measurements will then be obtained (about five additional minutes) with the subject sitting upright and no pressure applied to the back.

Next, the subject will be asked to lay supine on the first of four randomly assigned litter mattress combinations. Because the litters will be resting on top of stands, special care will be taken by study team members to ensure subjects safely mount and dismount litters without injury. Subjects will be secured to the litters in accordance with Aeromedical Evacuation Equipment Standards (AFI10-2909, 23 July 2013 pages 73-74).

"5.4.4.1. The patient is placed on the litter, covered with the sheet and blanket as necessary, and secured to the litter with 2 litter straps. The straps are placed mid-thigh and on the upper chest of the patient. Secure the litter straps so the buckles are on the aisle side of the litter, and lay the excess strap flat over the patient. DO NOT tie the excess strap in a knot. Litter straps will be visible for inspection.

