5.4.4.2. A mattress pad is recommended to prevent skin breakdown."

After the subject is positioned comfortably on the litter, the pressure mapping will begin. The peak interface pressure (the highest average pressure (mm Hg) measured over each

For Protocol Office use only:

Protocol title: NATO Litter: Fluid Immersion System
(FIS) versus Traditional Mattress for Pressure Dispersion
FDG20160005H wAmd5

(investigator names redacted 23 Jan 20)

DGMC Human Research Protocol

body region) will be measured for the occiput, sacrum, bilateral scapula, buttocks and heel areas. The total body surface area exposed to skin interface pressure greater than 30mm Hg will also be measured in centimeters squared (cm²) for each body region. Measures of tissue perfusion using the tcpO₂ in mmHg will be measured for comparison to baseline data. This process will take approximately twenty minutes for each of the four iterations. An additional 30 minutes is required to change the litter and mattress configurations. After baseline data are captured and tcpO₂ measurements are taken with the subject supine on all four litter/mattress combinations, the session is complete. Data from subjects who do not complete all four litter/mattress combinations will be excluded from the analysis. An estimated 25% attrition rate is factored into this study to ensure that 43 completed data sets are obtained.

6.5. Risks/Benefits:

- There is a potential risk of injury from falling off the litter while attempting to mount or dismount. This risk will be minimized by having a member of the research staff present whenever a subject is on the litter. Staff will be available to assist participants on and off the litter. A step stool will also be available to assist participants in safely mounting and dismounting the litter.
- There is also a potential risk of skin reaction to the adhesive which will hold the transcutaneous oxygenation transducers in place. If a participant shows signs and/or symptoms of skin irritation from the adhesive (redness, itching, rash or hives), the adhesive will be removed and the participant will be encouraged to see their primary care provider if the signs and/or symptoms do not quickly resolve or becomes worse after the adhesive is removed. If the participant's initial reaction to the adhesive pads is severe (difficulty breathing, face/lips, throat swelling, loss of consciousness) the subject will be taken to the DGMC Emergency Department for treatment.

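### Optional, unrecorded bra wear partly confounds the men-versus-women comparison at the scapular sites (minor)

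*Combined protocol and SAP*

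**What the plan says.** **Clothing (section 6.4).** The general rule is "Subjects will be asked to wear a nonrestrictive single layer of garments for the study". For the upper body, "They will be given a hospital gown to wear over the upper body", so that staff can reach the back to place the oxygen transducers. The exception follows: "Females will not be required to remove their bra". A bra kept on under the gown is a second layer.

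**Measurement (section 6.4).** Peak interface pressure "will be measured for the occiput, sacrum, bilateral scapula, buttocks and heel areas", and the area above 30 mmHg "will also be measured in centimeters squared (cm²) for each body region". Counting left and right separately, that is eight sites, two of them scapular. Section 6.3 defines the PPI as an average over eight cells, so that one faulty sensor does not drive the reading.

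**Hypotheses (section 6.3).** Hypothesis 2 states: "There is a difference in pressure distribution between men and women, given BMI level (high, ideal) for subjects on the WELP padded". Hypothesis 3 states: "There is a difference in pressure distribution between men and women, given BMI level (high, ideal) for subjects on the Dolphin FIS padded". Neither excludes a site.

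**Recording and analysis (section 6.8).** The table of research material lists demographics, BMI, height, weight, pressure mapping and tcpO2. It has no entry for bra use. The analysis is a repeated-measures ANOVA with within and between factors. No garment term or sensitivity analysis is mentioned.

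**The concern.** A strap, band or clasp can lie between the skin and the mat at or near the scapulae. If it changes the local reading, it does so in women only. Sex is a between-subject factor, so using subjects as their own controls does not remove the effect, and neither does stratifying on BMI. A larger sample would only estimate the mixture of sex and garment more precisely. Because wearing is optional and unrecorded, the effect also varies among women in a way that cannot be adjusted for afterwards. It could create an apparent sex difference at the scapulae or hide a real one.

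There is a smaller, second exposure. The surface and litter contrasts are within-subject, so a constant garment largely cancels. The plan does not require it to be constant, and section 6.4 allows a subject's session to be split over several visits.

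**Working it through.** The plan gives no figure on this point, so there is nothing to reproduce. The structure is checked by reading, and the size is illustrated under assumptions.

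**Which comparisons are exposed**
- Men versus women, scapular PPI and scapular area above 30 mmHg: exposed. The garment occurs in one sex only and is not recorded.
- Men versus women at the occiput, sacrum, buttocks and heels (six of eight sites): not directly affected.
- WELP versus FIS, and NATO versus Raven: protected if each woman makes the same choice on all four surfaces, which is not required.

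**How far the eight-cell average helps.** Section 6.4 gives half-inch cells. Eight cells cover 8 × 0.25 = 2 square inches, about 13 cm². A feature narrower than that is averaged with its surroundings, so it is dampened. A band or clasp that spans several neighbouring cells is not removed.

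**Illustration**

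From the documents: 43 evaluable subjects; two-sided significance level 0.05 (section 6.6).

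Assumed, because the documents do not say: a 22 versus 21 split by sex; between-subject SD of scapular PPI of 10 or 15 mmHg; no true sex difference; a shift of 3, 5 or 10 mmHg in each wearer; all or half of the women wearing a bra.

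Standard error of the sex difference = SD × √(1/22 + 1/21):
- SD 15: 15 × 0.305 = 4.58 mmHg
- SD 10: 10 × 0.305 = 3.05 mmHg

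Shift in the women's mean = share wearing × shift per wearer. The probability of a false sex finding is P(|Z + mean shift/SE| > 1.96).

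| Shift per wearer | All wear, SD 15 | All wear, SD 10 | Half wear, SD 15 | Half wear, SD 10 |
|---|---|---|---|---|
| 3 mmHg | 10% | 17% | 6% | 8% |
| 5 mmHg | 19% | 37% | 8% | 13% |
| 10 mmHg | 59% | 91% | 19% | 37% |

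Example: 5 mmHg per wearer with half wearing gives a mean shift of 2.5 mmHg. At SD 10, 2.5/3.05 = 0.82 and the rejection probability is about 13%.

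This is a normal-approximation two-group test, not the planned ANOVA with BMI level. It also ignores the small extra variance among women when only some wear the garment. It shows orders of magnitude only.

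**The case against.** The strongest case on the other side has five parts.

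1. **Sex is peripheral.** The major aim, both secondary aims and all four research questions concern mattresses and litters. Sex enters only through Hypotheses 2 and 3 and the sampling strata. This stands, and it sets the severity.

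2. **The mechanism is inferred.** Nothing in the documents says where a strap or band lies relative to the measured prominence, or whether it raises or spreads pressure. The eight-cell average dampens narrow features. Transducers are fixed in the scapular region in both sexes and may already dominate a peak-type index there. All of this stands against any claim about size or direction. It does not restore comparability between the sexes.

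3. **The hypotheses are ambiguous.** Their wording refers to the NATO with the Raven litter. If they ask whether the litter difference varies by sex, a garment worn consistently largely cancels. That is a possible reading. But the text states a difference between men and women, and consistency is not required anyway.

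4. **The exception is a reasonable privacy accommodation.** Agreed; nobody need be required to undress.

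5. **Stronger inferences go too far.** A reader might infer that every sex comparison is compromised, that any summary over sites carries the artefact, or that the scapular sites must be dropped. The documents do not support these. Six of eight sites are not directly affected. Measurement is specified by region, and no cross-site PPI summary is planned; a total area that included the scapulae would carry the effect only in diluted form. Dropping planned sites for an effect of unknown size is a debatable trade when recording bra use is cheap.

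**Conclusion.** The concern holds in a limited form. A between-sex comparison of scapular PPI or scapular area above 30 mmHg under Hypotheses 2 and 3 is partly confounded with a garment that only women can be wearing, and the planned data do not allow the two to be separated. Confidence is high in this structure and low in the size and direction, which the documents do not give.

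Under the assumptions above, the false-positive rate runs from about 6% to 37% if half the women wear a bra and from about 10% to 91% if all do. A reader might take the 59% and 91% as expected error rates. They need a 10 mmHg shift in the women's mean, and nothing in the documents supports that figure. Nor does the point undermine the WELP versus FIS comparison, provided each woman's garment stays the same on all four surfaces.

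Severity is minor.

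**What to change.** **In section 6.4:**
- Ask women, where willing, to unfasten the bra and move it off the scapulae under the gown, or to wear a top without straps or fasteners.
- Require the same choice on all four surfaces, including when visits are split.

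**In section 6.8:**
- Add a tick box for bra use to the data sheet.
- Keep the scapular sites. Report the scapular sex comparison with and without the women who kept the bra on, and state in advance that a scapular difference will not be attributed to sex alone if the two results disagree.

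**Cost:** one procedure line, one tick box and one sentence of analysis. Some women may decline, and the sensitivity analysis will have fewer women. If nearly all keep the bra on, it will say little, and the scapular sex result should then be described as possibly reflecting clothing. Women who keep it on may also differ in other ways, so the comparison is a check and not an adjustment.
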